## 1. INTRODUCTION

### 1.1 MEDICAL BACKGROUND

Systemic Sclerosis (SSc) is a devastating disease of unknown etiology. The pathogenesis of SSc is characterized by systemic (multi-organ) immunological, vascular and fibrotic abnormalities. It is a rare disorder, an orphan disease, with prevalence rate of approximately 50 to 300 in US, 20 to 50 in Asia and 100 to 200 per million in Europe ([R14-4918](#), [R14-4927](#)).

Patients suffer from multiple organ fibrosis, leading to chronic disability and premature death. Aside from skin, the lung is most often involved, but the disease may also manifest as proliferative and obliterative vascular abnormalities, kidney disease, oesophageal and gastrointestinal involvement (hypomotility), cardiac disorders and muscle disease. SSc-related mortality is mainly driven by interstitial lung disease and pulmonary arterial hypertension. Median survival is 5–8 years in SSc associated Interstitial Lung Disease (ILD) ([P14-07919](#)).

At time of writing the Protocol, no approved SSc treatment was available, for chronic treatment of SSc-ILD. To date, nintedanib is the only drug approved in several countries for the treatment of patients with scleroderma-associated interstitial lung disease (SSc-ILD). Immunosuppressive therapy has been proposed as a treatment of SSc with limited controlled data.

According to the EULAR treatment guidelines ([P15-00879](#)) there are no therapies mandated for SSc-ILD. Cyclophosphamide, a lymphocyte-modulating agent, may have some effect on forced vital capacity (FVC) ([R14-5407](#)). EULAR recommends considering cyclophosphamide for the treatment of SSc-ILD, but its use is limited in regard of treatment duration due to its toxicity. Methotrexate may be considered for treatment of skin manifestations of early diffuse SSc ([P15-00879](#)). Small controlled, uncontrolled and retrospectively controlled studies suggest some immunosuppressive regimens (such as mycophenolate, azathioprine, tocilizumab, ciclosporine A) may have effect in selected manifestations of SSc. However, larger placebo-controlled studies are lacking ([P15-00879](#)). Endothelin receptor antagonists failed to show significant effects on pulmonary fibrosis outcomes in several large studies.

The rationale for development of nintedanib in SSc-ILD is based on the pre-clinical evidence of potential effects in SSc and clinical evidence of antifibrotic activity of nintedanib in Idiopathic Pulmonary Fibrosis (IPF) along with an acceptable safety profile. Investigation in a patient population with active SSc-ILD accompanied by varying degrees of skin and other organ fibrosis is medically rational. Nintedanib may offer a long term antifibrotic maintenance treatment option for SSc, a medical indication with high unmet medical need.

The herein described clinical trial is planned as an open label extension trial following SENCIS® (1199.214) and 1199-0340 respectively.

The phase III trial SENCIS® (1199.214) was investigating and has proven the safety and efficacy of nintedanib in Systemic Sclerosis interstitial lung disease ([P19-04387](#)).

The phase I trial 1199-0340 was investigating the drug-drug interaction of nintedanib and oral contraceptives in female patients with SSc-ILD ([c26582112](#)).

In the following, the acronym SENCIS® will be used for trial 1199.214, standing for Safety and Efficacy of Nintedanib in Systemic Sclerosis (EudraCT no. 2015-000392-28).

## 1.2 DRUG PROFILE

Nintedanib is a small molecule that inhibits a distinct spectrum of receptor tyrosine kinases (RTKs) and non-receptor tyrosine kinases (nRTKs) including VEGFR (vascular endothelial growth factor receptor), PDGFR (platelet-derived growth factor receptor), FGFR (fibroblast growth factor receptor), and Src family kinases (Src, Lck and Lyn belonging to a family of proto-oncogene tyrosine-protein kinases).

All of these growth factor pathways and their down-stream signal cascades have been demonstrated to be involved in the pathogenesis of fibrotic tissue remodelling.

In experiments with dermal fibroblasts from patients with SSc, nintedanib inhibited migration and proliferation, reduced the expression of extracellular matrix markers, and attenuated transformation to myofibroblast. In four animal models of SSc with different features, nintedanib effectively attenuated skin and lung fibrosis, reduced extracellular matrix deposition in skin and lung, attenuated myofibroblast accumulation in skin and lung and reduced dermal thickening. Nintedanib also reduced dermal microvascular endothelial cell apoptosis and effectively attenuated pulmonary vascular remodelling by reducing the number of vascular smooth muscle cells and occluded pulmonary vessels.

A soft gelatin capsule formulation of nintedanib is used in humans. Maximum plasma concentrations occur between 2 - 4 hours after oral administration. Steady state is reached at latest within one week of dosing. After food intake, a trend towards an increased systemic exposure (around 20%) and a delayed absorption was observed compared to administration under fasted conditions. Nintedanib is preferentially distributed in plasma with a blood to plasma ratio of 0.87 and the terminal half-life is in the range of 7 to 19 h. The absolute bioavailability of nintedanib is slightly below 5%.

Nintedanib is mainly eliminated via faeces.

Coadministration of nintedanib with the P-glycoprotein (P-gp) inhibitor ketoconazole increased exposure to nintedanib by 60-70% based on area under the curve (AUC) and by 80% based on a maximum measured concentration of the analyte in plasma (Cmax) in a dedicated drug-drug interaction (DDI) trial.

In a DDI trial with the P-gp inducer rifampicin, exposure to nintedanib decreased to 50.3% based on AUC and to 60.3% based on Cmax upon coadministration with rifampicin compared to administration of nintedanib alone.

The clinical efficacy of nintedanib has been studied in over 1400 patients with IPF in one phase II dose finding trial (TOMORROW) including four different doses of nintedanib, and two replicate phase III (INPULSIS® 1 and 2) trials. These were randomised, double-blind, placebo-controlled trials comparing treatment with nintedanib twice daily to placebo for 52 weeks. A statistically significant reduction in the annual rate of decline of FVC (in mL) was demonstrated in patients receiving nintedanib 150 mg bid compared to patients receiving placebo. The treatment effect of nintedanib 150 mg bid compared to placebo on FVC was consistent in all 3 studies, i.e. a relative reduction of decline of approximately 50%.

Supporting the effect of nintedanib on slowing disease progression ([P14-07514](#), [P11-11216](#)), nintedanib 150 mg bid significantly reduced the risk of first acute exacerbation compared with placebo in INPULSIS® 2 and in the TOMORROW trial and reduced the risk of acute exacerbations (adjudicated) by 68% in a pre-specified sensitivity analysis of pooled data from the INPULSIS® trials.

In the Phase III trial 1199.214 (SENSCIS®) in patients with SSc-ILD, nintedanib, at a dose of 150 mg bid, significantly reduced the annual rate of decline in ██████████ after 52 weeks of treatment. The relative treatment effect, of a ~44% reduction in the annual rate of FVC decline compared with placebo, was in the same range as that previously observed in IPF. No effect of nintedanib on skin fibrosis or health-related quality of life was observed. No effect of nintedanib was seen on skin thickness and in patient-reported outcomes. There was no difference in mortality between the groups; however, the trial was not powered to detect such difference.

The safety profile of nintedanib has been investigated comprehensively in clinical Phase II to IV trials in patients with IPF, as well as postmarketing. The safety profile in phase III clinical trials in patients with SSc-ILD and patients with progressive fibrosing ILDs was generally consistent with that observed in the population of patients with IPF.

The risks of treatment with nintedanib in adult patients are primarily related to the gastrointestinal tract (nausea, vomiting, diarrhoea, abdominal pain, pancreatitis) and to drug induced liver injury/increases in liver enzymes (aspartate aminotransferase [AST], alanine transaminase [ALT], alkaline phosphatase [ALK], gamma-glutamyl transferase [GGT] and bilirubin).

Based on data from clinical trials and post-marketing with nintedanib in IPF patients and supported by population pharmacokinetic models, patients with low body weight (<65 kg), Asian and female patients have a higher risk of liver enzyme elevations with nintedanib treatment.

The most frequently reported adverse event in the clinical trials was diarrhoea, which was mild to moderate in intensity for the majority of patients and led to treatment discontinuation

in less than five percent of patients treated with nintedanib. Nausea, vomiting and weight decrease and decreased appetite have also been associated with nintedanib treatment.

Risks of nintedanib treatment also include hypertension, bleeding, thrombocytopenia, gastrointestinal perforations, and thromboembolism. Thus, patients treated with full-dose anticoagulation or at known risk for bleeding were excluded from the INPULSIS® trials. Although cardiac disorder adverse events were balanced between the nintedanib and placebo groups, a higher proportion of patients (1.6%) in the nintedanib groups had myocardial infarctions compared to the placebo groups (0.5%). Conversely, a lower proportion of patients in the nintedanib groups had other ischemic heart disease, which includes terms such as coronary artery disease, angina pectoris, coronary angioplasty, coronary artery stenosis, myocardial ischemia, coronary artery stent insertion, electrocardiogram (ECG) ST segment depression. The clinical significance of this finding is unknown, and further observation is needed. No imbalances were found in SENSISCIS®.

No evidence of QT prolongation was observed for nintedanib in the clinical trial program. As some tyrosine kinase inhibitors are known to exert an effect on QT, caution should be exercised when administered nintedanib in patients who may develop QT prolongation.

For patients finalizing the 52 week trial treatment in the TOMORROW and INPULSIS® trials, participation, open label extension trials (1199.35 and 1199.33) were offered. Long term treatment in these open label extension trials have confirmed the safety profile observed in the phase II and III trials.

Nintedanib was developed in Idiopathic Pulmonary Fibrosis (IPF) and approved by Food and Drug Administration (FDA) and European Medicines Agency (EMA) in October 2014 and January 2015 respectively.

Nintedanib was developed in Systemic Sclerosis associated ILD and approved by Food and Drug Administration (FDA) and European Medicines Agency (EMA) in September 2019 and April 2020 respectively.

See also Investigator's Brochure (IB) nintedanib in Idiopathic Pulmonary Fibrosis, Systemic Sclerosis, Progressive Fibrosing Interstitial Lung Disease ([c01783972](#)) for more details.

### 1.3 RATIONALE FOR PERFORMING THE TRIAL

The aim of this extension trial is to provide nintedanib treatment for all patients who have completed (did not prematurely discontinue trial medication) the phase III parent trial SENSISCIS® or the phase I trial 1199-0340 and who may have experienced benefit from the trial medication and wish to receive treatment.

This extension trial is designed to evaluate long term tolerability and safety of Nintedanib and the survival in SSc-ILD patients treated for a longer period of time. In addition, lung function

tests and assessment of the modified Rodnan Skin Score as well as patient and physician reported outcome measures will be performed.

#### 1.4 BENEFIT - RISK ASSESSMENT

Initiating and amplifying events in SSc-ILD and IPF are described to be different, but culminate in fibroblast activation and myofibroblast accumulation that represent the final common pathways of lung fibrosis in both SSc-associated ILD and IPF ([P14-07919](#)). Nintedanib inhibits migration, proliferation and transformation of fibroblasts and thereby addresses this common pathway.

As shown for IPF patients, patients with SSc-ILD may also benefit from lesser decline in lung function and hence slower disease progression as a result of treatment with nintedanib.

The safety profile and the tolerability of nintedanib are expected to be similar in patients with IPF and SSc-ILD.

Based on the efficacy and safety shown in IPF patients, and considering the similarity of the pharmacological rationale between IPF and SSc, the same dose regimen of 150 mg nintedanib bid is considered appropriate.

The risks of treatment with nintedanib have been well delineated in patients with the fibrotic lung disease IPF. These risks are primarily related to the gastrointestinal tract (nausea, vomiting, diarrhoea, abdominal pain), and are usually managed with supportive therapy and with temporary or permanent dose reduction to 100 mg bid. In some cases, temporary interruption or permanent drug discontinuation is necessary. A reduction in appetite and weight decrease has also been reported in patients treated with nintedanib. Patients with SSc may already suffer from gastrointestinal symptoms and will be monitored for such events. Parenteral fed patients will be excluded from the trial.

Drug induced liver injury, increases in liver enzymes and bilirubin have been reported with the use of nintedanib and liver enzymes must be followed closely during treatment (see also [Section 4.2.1.2](#)). Nintedanib must be dose-reduced, or interrupted in the event of hepatic toxicity and further treatment withheld until recovery of the abnormal laboratory parameters.

Concomitant therapies with a known overlap in side effects with nintedanib (e.g. gastrointestinal [GI] adverse events, increase of AST, ALT, bilirubin) or concomitant use of therapies that interact with metabolism of nintedanib (through UGT1A1 and P-gp) should be used with caution and patients should be closely monitored (see [Section 4.2.2.2](#)).

Potential risks of nintedanib treatment also include gastrointestinal perforations, thromboembolism and bleeding. Therefore, patients who have planned major elective surgery, suffer from severe peripheral vascular disease, requiring full dose therapeutic anticoagulation, fibrinolysis or high-dose antiplatelet therapy will be excluded from this trial. Patients with severe pulmonary hypertension, Child Pugh A/B/C and Scleroderma renal crisis will not be included in this trial. Those patients will either not have been included in the

parent trial as per Inclusion/Exclusion criteria or discontinued in the parent trial due to these conditions occurring as adverse events.

The mode of action of nintedanib indicates a high potential for teratogenicity and embryotoxicity, including fetotoxicity and lethality. In women of childbearing potential receiving nintedanib, contraceptive measures must be employed 28 days before treatment initiation, during the treatment and for a period of 3 months after last drug intake.

To address the organ-specific manifestations, immunosuppressive agents (e.g. mycophenolate, cyclophosphamide, methotrexate, azathioprine, prednisone) are commonly used and need to be considered although appropriate randomised-controlled data for these therapies are lacking.

The concomitant use of immunosuppressive agents as well as of non-immunosuppressive therapies for other SSc manifestations as for digital ulcers (e.g. bosentan), GI symptoms (e.g. proton pump inhibitors, prokinetic drugs), renal crisis (e.g. angiotensin-converting-enzyme inhibitor [ACE inhibitors]), pulmonary hypertension / pulmonary arterial hypertension (PH / PAH) (e.g. bosentan, sildenafil, epoprostenol) are not restricted. Cautionary notes are included in the protocol ([Section 4.2.2.2](#)) with regard to such therapies whose safety profile could interfere with that of nintedanib.

Safety of the patients will be monitored at site visits, including physical examinations, safety laboratory and specific monitoring procedure to follow-up potential hepatic enzyme elevation, to exclude pregnancy, to follow-up electrocardiographic assessments, and to monitor blood pressure, renal function, hypertension, and digital ulcers. Treatment with nintedanib must be discontinued and appropriate therapeutic measures taken in patients who develop severe symptoms of gastrointestinal toxicity not amenable to symptomatic treatment with standard measures or severe liver enzyme elevations or other severe adverse events as specified in [Section 3.3.4](#).

Even if the balance of safety and efficacy from SENSISCIS® is still unknown at the time point the patients are rolled over into the open label extension trial, long-term treatment is considered justifiable as there is currently no pharmacotherapy for long-term use approved to modify or prevent systemic progression of SSc/SSc-ILD.

To address current practice (although randomised-controlled data for these therapies are scarce), patients on a stable background therapy of mycophenolate, methotrexate or low dose prednisone were eligible in SENSISCIS®.

In trial 1199-0340 patients on certain background therapy including mycophenolate and other treatments were excluded due to their potential effect on the PK assessment.

Continuation or initiation of immunosuppressives or other treatments or changes in their dose is allowed in the open label extension taking into consideration cautionary notes.

All patients will receive active treatment in this trial. Patients who were randomized to placebo in SENCIS® will be receiving the active drug for the first time. Therefore the same close monitoring will be conducted as in SENCIS® for the first 3 months of the trial.

Based on the pharmacological mechanism, existing non-clinical, clinical and post-marketing data there is no indication that treatment with nintedanib may increase the risk for infection with SARS-CoV-2 or for worsening the disease course of COVID-19.

It is currently unknown if SSc or SSc-LD conveys a higher risk for adverse outcomes in case of COVID-19.

The trial related risk to the COVID-19 pandemic situation is the general risk of travelling to site and being at site for assessments with increased infection risk for lung function testing. Risk mitigation and possible modifications are described in [Section 6.1](#) and in [Appendix 10.3](#)

The extrapolated benefit risk ratio of chronic treatment with nintedanib 150 mg bid, with the possibility to be interrupted or reduced to nintedanib 100 mg bid during periods of intolerability, is judged positive for patients with SSc-ILD.

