### **3.3.4 Withdrawal of patients from therapy or assessments**

#### **3.3.4.1 Withdrawal from trial treatment**

Nintedanib has to be permanently discontinued in the following circumstances

- The patient experiences signs of hepatic injury, defined in [Section 4.2.1.2](#)
- In the opinion of the investigator, the patient experiences unacceptable adverse events despite dose adjustments and supportive care.

- Use of concomitant treatment as defined in [Section 4.2.2](#).
- Parenteral feeding requirement.
- The patient can no longer be treated with trial medication for other medical reasons
- The patient has repeatedly shown to be non-compliant with important trial procedures and, in the opinion of both, the investigator and sponsor representative, is not willing or able to stick to the trial requirements in the future
- Pregnancy (refer to [Section 5.2.11](#))
- If a patient becomes pregnant during the trial, nintedanib needs to be stopped and the patient should be followed up until birth or otherwise termination of the pregnancy. The data of the patient will be collected and reported in the clinical trial report (CTR) until patient's last visit and any events thereafter will be reported in the BI drug safety database. Refer to [Section 5.2.11](#) for detailed information on event reporting in case of pregnancy.

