#### **4.2 OTHER TREATMENTS, EMERGENCY PROCEDURES, RESTRICTIONS**

##### **4.2.1 Other treatments and emergency procedures**

Rescue medications to reverse the action of nintedanib are not available.

Dose reduction (from 150 mg bid to 100 mg bid) or treatment interruption should be considered to manage adverse events. No further dose reduction is possible for patients on the 100 mg bid dose. In case of persistent adverse events observed at this dose, or severe effects at 150 mg bid, permanent treatment discontinuation should be considered.

Treatment interruption and reduction and reescalation are repeatedly possible.

Table 4.2.1: 1 Allowed treatment reduction / interruption periods:

	AEs considered drug related	AEs or other events not considered drug related
Maximum interruption	4 weeks	12 weeks
Recommended restart	with reduced dose (100 mg bid)	with the same dose (100 mg bid or 150 mg bid)
Re-escalation	Any time to 150 mg bid	----

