Diarrhoea with increase of $\geq 7$ stools per day over baseline  ; stool incontinence, or life threatening consequences.	Follow recommendations above. In addition, consider stool work-up to exclude infectious colitis; adequate IV fluid replacement $\geq 24$ hours, hospitalisation as clinically indicated; consider referral to a GI specialist to rule out potential differential diagnoses.	
 
1. Interrupt trial medication until recovery.
 
2. Reduce dose to 100 mg bid after recovery.
 
3. Consider re-escalation within 4 weeks to 150 mg bid if deemed clinically appropriate.
 
 In case of reoccurrence of diarrhoea of this severity despite optimal symptomatic treatment and dose reduction, treatment with trial medication should be permanently discontinued.

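### For severe diarrhoea not controlled by symptomatic treatment, protocol Section 1.4 requires discontinuation while Table 4.2.1.1:1 directs interruption, reduction and possible re-escalation; recurrence after re-escalation is also unclear

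*Protocol*

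**What the plan says.** Four places in the current protocol bear on what happens to trial medication in severe diarrhoea.

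- **Section 1.4 (benefit-risk).** "Treatment with nintedanib must be discontinued and appropriate therapeutic measures taken in patients who develop severe symptoms of gastrointestinal toxicity". The full trigger is "severe symptoms of gastrointestinal toxicity not amenable to symptomatic treatment with standard measures". The sentence continues "or severe liver enzyme elevations or other severe adverse events as specified in" and ends with a link to Section 3.3.4.
- **Section 3.3.4.1 (withdrawal from treatment).** Permanent discontinuation is required when, in the investigator's opinion, "the patient experiences unacceptable adverse events despite dose adjustments and supportive care". No criterion is worded for severe gastrointestinal toxicity or diarrhoea.
- **Section 4.2.1 (general rule for any adverse event).** For persistent events at 100 mg bid, or "severe effects at 150 mg bid, permanent treatment discontinuation should be considered". The section adds: "Treatment interruption and reduction and reescalation are repeatedly possible".
- **Section 4.2.1.1 and Table 4.2.1.1:1 (diarrhoea considered drug-related).** If optimal symptomatic treatment fails, interruption and dose reduction are to be considered as the table recommends. Its most severe row covers at least 7 extra stools per day, incontinence and life-threatening consequences. The steps are to interrupt until recovery, then reduce to 100 mg bid, then "Consider re-escalation within 4 weeks to 150 mg bid if deemed clinically appropriate". The row closes: "In case of reoccurrence of diarrhoea of this severity despite optimal symptomatic treatment and dose reduction, treatment with trial medication should be permanently discontinued".

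**The concern.** Section 1.4 and Section 4.2.1.1 start from nearly the same situation, severe gastrointestinal symptoms that symptomatic care has not controlled, and lead to different actions. One stops the drug. The other pauses it, brings it back at a lower dose and leaves the way open to the full dose. A site could follow either and believe it was following the protocol, including after a life-threatening episode, because the severe row does not separate that case.

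The first stake is patient safety: a protection stated in the benefit-risk section is not carried into the table that sites use. The second is the safety output. SAP Section 7.8.1 tabulates adverse events leading to discontinuation, dose reduction and interruption. Section 7.8.1.4 summarises the clinical consequences of diarrhoea, and Section 7.7 plots time to permanent discontinuation. All of these record the dose action chosen, so part of what they show would reflect which section a site followed. Protocol Section 1.2 names diarrhoea as the most frequently reported adverse event in the clinical trials.

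**Working it through.** No arithmetic applies. The check sets trigger against action in each place and asks where the triggers overlap.

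1. **Section 1.4.** Trigger: severe gastrointestinal symptoms that standard symptomatic measures do not control. Action: discontinue (mandatory).
2. **Section 4.2.1.1 and the severe table row, first episode.** Trigger: drug-related diarrhoea of the worst category, with the lead-in text addressing failure of optimal symptomatic treatment. Action: interrupt, reduce, possibly re-escalate.
3. **Severe table row, recurrence.** Trigger: the same severity again despite symptomatic treatment and dose reduction. Action: permanent discontinuation.
4. **Section 4.2.1.** Trigger: any severe effect at 150 mg bid, or persistent events at 100 mg bid. Action: consider permanent discontinuation. Repeated cycles of interruption, reduction and re-escalation are allowed.
5. **Section 3.3.4.1.** Trigger: unacceptable events after both dose adjustment and supportive care. Action: permanent discontinuation.

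**First episode.** Items 1 and 2 overlap for a first severe, refractory episode. Item 1 requires a stop; item 2 requires a pause and a return to treatment. Item 4 does not decide between them, since considering discontinuation is compatible with either.

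**Can the link to Section 3.3.4 remove the conflict?** It has two readings.
- If it governs the whole sentence, Section 3.3.4 should contain the gastrointestinal rule. The nearest one, item 5, needs failed dose adjustment as well as failed supportive care. Section 1.4 needs only failed symptomatic treatment. The two triggers differ, so Section 1.4 misdescribes the section it cites.
- If it governs only the other severe adverse events, Section 1.4 is a free-standing mandatory rule and conflicts directly with item 2.

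Under either reading one of the texts has to change.

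**Life-threatening episodes.** Table 5.2.11.1:1 separates CTCAE grade 3 (at least 7 extra stools, incontinence) from grade 4 (life-threatening). The severe row of Table 4.2.1.1:1 merges them, so a life-threatening first episode follows the same interrupt, reduce and possibly re-escalate sequence.

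**Recurrence.** At 100 mg bid, item 3 applies on its face. After re-escalation to 150 mg bid the reduction has been reversed. It is then unclear whether the episode counts as recurring despite dose reduction (item 3, stop) or as the start of another permitted cycle (item 4).

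**Would divergent handling be detected?** SAP Table 6.2:1 has deviation codes C2 and C3 for failing to interrupt or discontinue after liver enzyme elevations. It has no counterpart for gastrointestinal events.

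**The case against.** The strongest reply is that the text forms a workable ladder. The diarrhoea table is the specific rule. It runs from symptomatic care through interruption and reduction to permanent discontinuation on recurrence, and that last step fits Section 3.3.4.1. Elsewhere Section 1.4 describes gastrointestinal risks as usually managed with supportive therapy and dose reduction, and its closing judgement relies on the option to interrupt or reduce. On this view the mandatory sentence is a loose summary. It also says discontinued without adding permanently, so it might mean a pause.

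Much of this stands. It shows that the benefit-risk case does not rest on that one sentence, and that the general wording in Section 4.2.1 need not oppose the table. It does not remove the conflict. The sentence is itself specific to gastrointestinal toxicity, is mandatory and points to the withdrawal section, and Section 1.4 uses interruption when it means a pause. If a pause was intended, the wording needs correcting.

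A reader might infer more than the documents support:

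- **That every severe diarrhoea has three contradictory dose actions.** Section 1.4 covers only refractory symptoms, and Section 4.2.1 only asks that discontinuation be considered. Adverse-event intensity is graded by function in Section 5.2.11.1, while the table uses stool counts, incontinence or threat to life, so the triggers are not the same event in general.
- **That Section 3.3.4 has no other criterion touching the gut.** Section 3.3.4.1 lists a need for parenteral feeding and a general medical-reasons criterion. Section 3.3.4.2 recommends stopping for gastrointestinal bleeding or ulcers and for abdominal surgery. None of these is a rule for refractory severe diarrhoea as such.
- **That the effect can be sized from the under five percent discontinuation figure in Section 1.2.** That is an upper bound from other trials, for diarrhoea of any severity, and nothing gives the number of cases that would be handled differently.

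**Conclusion.** The inconsistency is real and narrow. For a first episode of severe diarrhoea that symptomatic treatment does not control, Section 1.4 and Section 4.2.1.1 with its table give different actions, and Section 3.3.4 does not contain the rule that Section 1.4 appears to cite. For severe diarrhoea recurring after re-escalation to 150 mg bid, the table and Section 4.2.1 leave the action open.

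The conclusion on the first episode assumes that discontinued in Section 1.4 means stopping treatment, which is the natural but not the only reading. The point about recurrence does not depend on it.

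No numerical magnitude is claimed. The primary endpoint, the number and percentage of patients with any adverse event, counts the event whatever dose action follows. All analyses are descriptive, and investigator judgement would leave some variation between sites even with aligned text. The consequence falls on patient safety and on the interpretation of the discontinuation, reduction and interruption tables. It is worth correcting, but it does not undermine the trial.

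**What to change.** The sponsor should reconcile Section 1.4, Section 3.3.4.1, the text of Section 4.2.1, and Section 4.2.1.1 with the severe row of Table 4.2.1.1:1. They should state one consistent action for each of:

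- a first severe episode refractory to symptomatic care;
- a life-threatening episode;
- recurrence at 100 mg bid;
- recurrence after re-escalation to 150 mg bid.

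The link in Section 1.4 should then lead to text that contains the rule it describes. Which action applies in each case is a clinical decision for the sponsor, and none is proposed here. The cost is protocol wording, by amendment or clarification, and a notice to sites. The planned analyses need not change.
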